6.5.1.3 Secondary End-Point Analysis: Biomarkers

In this sub-aim, we hypothesize that molecular biomarkers will change (improve) with each treatment phase, at least in part. Furthermore, we hypothesize that biomarkers may reveal (a) novel insight into therapeutic resistance and/or relapse; (b) reveal patient sub-groups not identified by histology; and (c) ultimately prove to be readily usable biomarkers in clinical settings and possess personalized medicine value. We will focus on molecular profiling of esophageal genes with the Eosinophil Diagnostic Panel (EDP), a set of 94 mRNA transcripts that have been established to differentiate EoE from controls (e.g. GERD and normal individuals), and to identify exposure and transcriptional signaling to SGCs²⁹. The EDP is typically performed on an extra

biopsy taken from the distal esophagus²⁹. If our hypotheses are proven to be correct, this has potential to transform monitoring of patients during therapeutic intervention, by identifying molecular markers that have therapeutic significance, and also by reducing the need for biopsies, particularly after therapy is initiated. Essentially, the associated EDP algorithm renders the raw Ct values of each embedded gene after real-time PCR in a way that the upregulated genes and down-regulated genes are summed up individually. A quantitative “EoE score” is derived from the Δ Ct (normalized to GAPDH) summation to reflect disease severity and for statistical analysis. Utilizing different gene sets, EDP is also able to predict steroid exposure and remission status based on the same algorithm²⁹. In this case, the EoE score will be calculated at baseline endoscopy and in the post-treatment biopsies to assess change with treatment.

6.5.2 AIM 2: Clinical Parameters & Biomarkers That Predict Therapeutic Response

6.5.2.1 Clinical Phenotypes

In this sub-aim, we hypothesize that certain patient phenotypes will correlate with response to each intervention in the trial. We will assess the relationship between response to 1FED, 4FED, and SGC on age, height, weight, BMI Z-score, race, ethnicity, allergic status, participant compliance (defined by diet and SGC usage diaries), and screening eosinophil levels as readouts.

6.5.2.2 Skin Testing

In this sub-aim, we hypothesize that skin test results (prick testing and atopy patch testing to the four food groups) will provide significant predictive value for outcomes in the diet trial phases. While a substantial body of work has already been done concerning skin testing, there still remains debate about its practice in managing EoE. As such, in this sub-aim, we will take several different approaches compared with prior work. In particular, we will be conducting a multi-site trial and have the advantage that we can standardize the skin testing procedure, by using agreed upon techniques, including food extracts, skin test reagents, and measurement parameters. We will thus be in a good position to dissect discrepant results between centers. Furthermore, our trial is unique in that half of the patients will undergo a milk elimination diet as part of the first phase. Thus, we will be in a position to focus on the value of skin testing for milk, which is particularly attractive as milk is the number one food trigger of EoE³⁰. It is important to point out that although skin testing (including patch testing) is now readily performed in EoE, there have been no studies that have assessed the local response. For example, it has not yet even been determined if positive responses involve immunological reactions so basic cytokine and histological analyses are likely to be fundamentally informative.

6.5.2.3 Component Testing

Increased levels of food-specific IgE are present in patients with EoE yet their predictive value in guiding food

elimination diets for disease treatment is limited³¹. Recently, it has been proposed that the inability of food specific IgE tests to predict clinical reactivity may be related in part to the use of allergen extract reagents that do not contain the full set of relevant allergens. This diagnostic limitation has spurred the development of molecular diagnostic tests, referred to as component-resolved diagnostics (CRD), which utilize purified native or recombinant allergens to detect IgE sensitivity to individual allergen molecules; this also has the advantage as interactions between IgE sensitization and clinical reactivity can be examined, such as food-pollen cross-reactivity³²⁻³⁵. One of the goals of the present study is to examine the potential value of CRD in predicting diet outcomes in EoE. To address this goal, we will subject a baseline serum sample to CRD ImmunoCap (ThermoFischer Scientific); includes 3 egg components (Gal d 1 [ovomucoid], Gal d 2 [ovalbumin], and Gal d 3 [ovotransferrin]), and 4 milk components (Bos d 4 [alpha lactoglobulin], Bos d5 [beta lactoglobulin], Bos d8 [casein] and Bos d lactoferrin) as well as other foods and pollens when indicated. We will initially focus on the correlation between the presence of positive milk component (>0.1 kUA/L) and responsiveness in the group doing 1FED (milk elimination diet) because (a) this will provide proof-of-principle for other foods; (b) milk is the most common food that shows positive IgE in EoE patients³⁶; and (c) all patients in this group will undergo sole milk elimination and the results should be definitive concerning whether milk is indeed driving disease induction. With the wider range of CRD data, we will perform principal component analysis (PCA) to dissect the key allergens that are contributing to most of the variation. Similar to the way we process the EDP dataset, we also plan to derive personal heat-diagrams and present the CRD data in reviewable format by dimensionality reduction, such as multi-dimensional scaling (MDS) analysis. These approaches are expected to prioritize the key drivers in the component results and multiple statistical analyses can be subsequently investigated. For cost savings, serum samples from all cohorts will be analyzed in batches so we can determine if any trends are present before we analyze all samples.

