12 STATISTICAL METHODS

12.1 Sample Size Calculation

Sample size was determined based on the primary endpoint of the trial: The overall PEES score change from pre-treatment. Based on a preliminary report¹⁸ we estimate that 40-50% of patients may respond to 1FED as our study is prospective compared with 65% response in this preliminary retrospective report and based on food reintroduction trial results³⁰. Likewise, we would expect 75% of patients to respond to 6FED based on the previously reported studies, and from this we extrapolated a projected response of 65% to 4FED, given that the 4 eliminated foods are consistently identified as the most common triggering antigens³⁰. As such, we estimate that 45% of patients will respond to 1FED and wish to detect an additional 20% increase for the 4FED (i.e. 65% response rate). A non-parametric Wilcoxon rank sum test will be applied for the primary efficacy endpoint comparison. We are assuming a difference in response rate of 45% vs 65% between the two treatment groups, and we further assume that those who respond to 1FED will naturally respond to 4FED. We also assume that those who responded will have a higher PEES score change than those who do not respond. Then the estimated probability of 4FED scores higher than 1FED is about 0.60 ($= 0.5 \times \text{prob. of response to both or neither} + 1.0 \times \text{incremental response rate from 1FED to 4FED}$). This will require 131 patients per group to reach 80% power at 0.05 test level. By accounting for a 10% early dropout rate, we propose a sample size of 146 per group, or 292 total patients to be enrolled.

12.2 Statistical Analyses: Aim 1

Demographic and patient characteristics will be summarized for the two treatment groups using mean \pm standard deviation or median [interquartile range] for continuous variables and frequency and percentages for categorical variables. Treatment comparisons will be performed using the two-sample t-test or Wilcoxon Rank sum test for continuous variables and the Fisher's Exact test for categorical variables. All tests will be conducted at $\alpha=0.05$, including the primary and secondary analyses.

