2 STUDY DESIGN

This trial is comprised of 2 phases with each phase lasting 3 months. In the first phase, all participants will be randomized 1:1 to either 1FED or 4FED therapeutic diet. At the end of this phase, an EGD will be performed to assess histologic remission, which represents one of the primary current tools used in evaluating EoE disease activity during clinical trials and daily EoE care. Attainment of remission (esophageal eosinophil counts <15 eosinophils/high powered field) after Phase I will result in study discontinuation and maintenance of the “successful” dietary therapy. Dietary therapy non-responders who were on 4FED during Phase I will receive topical swallowed steroids for 3 months while on an unrestricted diet (Phase 2) followed by EGD with esophageal biopsies. Participants receiving SGC will return to an unrestricted diet (i.e. stop 4FED) prior to initiating SGC therapy. Dietary therapy non-responders who were on 1FED during Phase 1 will proceed to 4FED for 3 months (Phase 2) followed by EGD with esophageal biopsies.

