4 STUDY PARTICIPANTS

4.1 Number of Participants

A total of 292 participants between the ages of 6-17 years were to be enrolled. Because of unexpectedly slow

enrollment, the actual number of participants will be around 50 total. The DMCC at the University of South Florida Health Informatics Institute will serve as the central data management center, with CCHMC serving as the primary site and the central IRB. Additional sites include: Children's Hospital of Colorado, Riley Hospital for Children, Children's Hospital of Philadelphia, University of California at San Diego/Rady Children's Hospital, Northwestern University/Lurie Children's Hospital, Tufts Medical Center, Mt. Sinai Kravis Children's Hospital, Arkansas Children's Hospital, and the University of North Carolina.

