 - Percent of participants who achieve histologic remission (<15 peak eosinophils/HPF) post therapy assessed after the end of the 3 months
 - Division of patients into complete (all peak eosinophils ≤1/HPF) or partial (the worse of 3 scores is from 2 to 14) remission, and non-remission (at least one > 14/HPF)
 - Histology Scoring system
 - Endoscopic scoring system (EREFS)
- Biomarkers pre- and post-treatment
 - Assessment of Eosinophil Diagnostic Panel EoE Score
- Clinical parameters and biomarkers to predict responsiveness to diet and SGC therapy

- Correlation of clinical characteristics to response to therapy
- Assessment of predictive value of skin prick and patch allergy skin testing
- Correlation between presence of positive milk component allergy testing to response to 1FED
- Predictive biomarker-analysis of EoE transcriptome from EDP analysis on baseline biopsies in correlation to response to treatment.

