- (2) Remission rates will be compared between the two treatment groups using the generalized linear mixed effects model with the logit link (for binary outcome) that accounts for the clustering within sites. Important covariates will be analyzed in this model including gender, race, PPI use, atopy, age, and anthropomorphic features. Treatment group comparisons for secondary endpoints will be performed using the generalized linear mixed effects model using the link that is appropriate for the endpoint (i.e. logit for binary, log for Poisson count, identity for continuous). These models will account for the clustering within sites and will include the same covariates as for the primary analysis.
- (3) The remission rate for non-responders who proceed to Phase II will be summarized separately depending on the treatment patients received during Phase I and Phase II. The 95% confidence interval for the rates will also be provided.

6.2 Statistical Analyses: Aim 2

To evaluate the ability of biomarkers and phenotypic characteristics to predict response to therapeutic intervention, multivariable logistic regression analysis may be conducted with histological evaluation of remission/no remission as the dependent variable and biomarker levels as the independent variables. Multicollinearity of the independent variables will be assessed. The area under the receiver operating characteristic curve (AUROC) will be estimated along with 95% confidence interval. This analysis will be conducted based on the remission status at the end of Phase I. It may also be repeated at the end of Phase II by including those patients who also responded to SGC.

Additionally, a correlation analysis between PEES scores and biomarkers will be performed. Spearman's correlation coefficient and its confidence intervals will be computed to further assess predictive utility for the biomarkers of interest.

Missing data will be handled in the following manner. For the primary efficacy measure of PEES, each patient is expected to complete the questionnaire; even if the patient terminates participation early (dropout) for any reason. The total PEES score is the average of 20 item scores, as long as there are at least 10 item response non-missing, as described previously. No imputation of missing total PEES will be performed. The early dropout reasons will be recorded, and rates will be assessed between treatment groups for potential patterns.

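### The lead milk-component IgE analysis reduces both IgE and outcome to yes/no in about 25 children, losing power that the measured level and eosinophil count would partly recover

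*Protocol*

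**What the plan says.** Protocol 6.5.2.3 plans component testing on baseline serum, including four milk components, and starts with the "correlation between the presence of positive milk component (>0.1 kUA/L) and responsiveness in the group doing 1FED". It presents this as proof of principle for other foods. SAP 5.2 lists the same analysis as "Correlation between presence of positive milk component allergy testing to response to 1FED". Neither place names a test, defines response or gives a reason for the 0.1 cut. In the Aim 2 methods and the secondary objectives, response is histologic remission, meaning a peak count below 15/hpf.

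SAP 4.1 states that "the actual number of participants will be around 50 total", and SAP 2 that "all participants will be randomized 1:1 to either 1FED or 4FED therapeutic diet".

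Three other planned analyses use measured biomarker values:
- The Aim 2 logistic regression has "histological evaluation of remission/no remission as the dependent variable and biomarker levels as the independent variables". It is firm in Protocol 12.3 but optional in SAP 6.2.
- A Spearman analysis in the same sections pairs biomarkers with PEES.
- Protocol 6.5.2.3 plans principal component and scaling analyses of the wider component data.

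No section pairs milk-component IgE level with eosinophil count.

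**The concern.** The threshold is given in kUA/L, so a numeric result lies behind each positive or negative label. The cut treats a child just above 0.1 like a child many times higher. Remission is likewise a cut of a count that the plan already lists as an endpoint before and after therapy. What remains is a 2x2 table.

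At the planned 146 per arm this would have mattered less. At about 25, discarding information in both variables makes it more likely that a real association between milk IgE and response yields an inconclusive table. Because the analysis is meant to guide work on other foods, a false negative could carry beyond milk.

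**Working it through.** **Inputs from the documents.** About 50 children at 1:1 gives 50/2 = 25 on 1FED. For remission, "we estimate that 45% of patients will respond to 1FED", so about 11 of 25 remit and 14 do not. The test level is 0.05 (taken as two-sided).

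**Inputs not in the documents (assumed).** The share with a positive milk component is 30%, 50% or 70%. The true correlation r, in absolute value, between log IgE and log end-of-Phase-I count is 0.3, 0.5 or 0.6.

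**The plan's own figures.**
- *Primary sample size (Protocol 12.1).* P = 0.5 × 0.80 + 1.0 × 0.20 = 0.60. Noether: N = (1.96 + 0.8416)² / [12 × 0.25 × (0.60 − 0.50)²] = 261.6, or 131 per group. This matches "This will require 131 patients per group to reach 80% power at 0.05 test level". Dropout: 131/0.90 = 145.6, so 146, as stated.
- *Aim 2 (Protocol 12.3: at least 80% power for AUROC 0.60).* Power = Φ[(0.10 − 1.96·SE₀)/SE₁], with Hanley-McNeil standard errors at AUROC 0.50 and 0.60. For 161 in remission against 131 not, power is 84.4%. With 10% removed (145 against 118) it is 80.4%. The claim reproduces.
- *Same formula for the 1FED arm now (11 against 14).* Power is 12.8%.

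The documents give no power figure for the milk-component analysis itself.

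**Simulation of the milk analysis.** n = 25, bivariate normal on the log scale, 4,000 replicates per cell. IgE at or below the cut is set to the cut. The lowest 45% of counts are called remission. Power (%):

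| r | % positive | Cut IgE vs remission, Fisher | Same, chi-square | IgE level vs remission, Wilcoxon | IgE level vs count, Spearman |
|---|---|---|---|---|---|
| 0.3 | 30 | 10 | 16 | 15 | 20 |
| 0.3 | 50 | 13 | 16 | 16 | 24 |
| 0.3 | 70 | 10 | 14 | 19 | 28 |
| 0.5 | 30 | 26 | 36 | 35 | 49 |
| 0.5 | 50 | 33 | 38 | 43 | 61 |
| 0.5 | 70 | 25 | 32 | 48 | 67 |
| 0.6 | 30 | 40 | 51 | 51 | 67 |
| 0.6 | 50 | 49 | 54 | 62 | 80 |
| 0.6 | 70 | 35 | 46 | 65 | 85 |

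At r = 0 the rejection rate is about 3-4% for Fisher and about 5-6% for chi-square and Spearman. Part of Fisher's deficit is therefore conservatism.

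Tying the lowest 20% of counts at a floor, which is closer to real counts, gives at r = 0.5: Fisher 23-35%, chi-square 32-41%, Spearman 48-65%. At r = 0.3, Spearman runs about 19-29% across the floor settings.

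**Where the gain comes from.** At r = 0.5 and 30% positive, replacing only the IgE cut by the level gives 35% against 36% by chi-square, which is no gain. Replacing remission by the count as well gives 49%. At 70% positive, the level alone does help (48% against 32%).

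**A threshold effect instead.** Suppose only sensitised or not matters, with a 1.2 SD shift in the count. At 30/50/70% positive, chi-square on the cut variables has 57/64/48% power and Spearman with the count 66/71/49%. The gains are 9, 7 and 1 points. IgE level against remission has 52/54/31%, worse than the cut.

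**What 25 children can detect.** By Fisher's z, 80% power needs r = tanh[(1.96 + 0.8416)/√22] = tanh(0.597) = 0.54. An observed correlation of 0.3 would have a 95% CI of tanh(0.310 ± 1.96/√22), about −0.11 to 0.62.

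**Role of the reduced enrolment.** At 131 children, r = 0.4 and 50% positive, the cut analysis still has 82% (Fisher) to 85% (chi-square) power.

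**The case against.** The strongest reply has five parts.

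- *Measured levels are not discarded.* The Aim 2 regression, the PEES correlations and the component-space analyses all use them, and the protocol describes the milk table only as an initial focus. This stands in part. The regression is optional in the SAP, is not specific to milk IgE on 1FED and keeps yes/no remission. The Spearman analysis is against a symptom score. The component-space analyses do not test response.
- *The 15/hpf cut has a clinical basis.* It is the diagnostic criterion, the entry criterion, the remission definition and the rule for entering Phase II. This stands. A correlation with the count answers a related but different question, which is why the table should be kept.
- *The size depends on an assumed smooth relation.* This stands. Under a threshold effect the gain nearly disappears, though Spearman with the count was still no worse than the table.
- *Reduced enrolment is the main cause of low power.* This stands. The double cut makes it worse.
- *The plan does not tie this table to Fisher's test.* This stands. A reader might infer that it does from SAP 6.1, but that sentence concerns comparisons between the two diet groups, not an association within one arm. Chi-square figures are therefore given too.

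A reader might also infer that the protocol promises a definitive verdict on IgE as a predictor. The sentence in 6.5.2.3 is about whether milk drives disease in children who eliminate milk alone. Nor does any section say that a non-significant table would lead to the marker being dropped.

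**Conclusion.** The point holds in a limited form. The lead milk-component analysis cuts both variables in about 25 children, and no planned analysis pairs milk IgE level with eosinophil count. At an assumed smooth correlation of 0.5, Spearman of level on count has about 48-65% power, against 23-35% (Fisher) or 32-41% (chi-square). Under a threshold effect the gain over chi-square is about 1-9 points.

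It would be too strong to conclude that levels and counts would reveal a signal that the table misses. At correlation 0.3, Spearman reaches only about 19-29%, so it too misses the association in at least seven trials of ten. Much of the gain comes from using the count rather than from the IgE level alone.

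The positivity share, the correlation, the shape of the relation and the share of counts at the floor are assumptions. Dropout, or stopping after early serum batches as 6.5.2.3 allows, would lower n below 25. This is a secondary aim, and the primary comparison is not affected.

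**What to change.** In Protocol 6.5.2.3 and SAP 5.2:

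- Make the main milk-component analysis the Spearman correlation, with 95% CI, between baseline milk-component IgE and the end-of-Phase-I peak eosinophil count in the 1FED group.
- Name one IgE summary in advance: the highest of the four milk components, with values at or below 0.1 kUA/L set to 0.1. This also prevents a later choice among components.
- Label the analysis exploratory.
- Keep the table of positive (>0.1 kUA/L) by remission (<15/hpf) as the clinically readable descriptive summary.

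The cost is wording only. Baseline component testing and peak counts are already planned, and the SAP describes itself as fixed before the database is final. The downsides are that a correlation gives no positive/negative rule and that the analysis remains underpowered unless the true correlation is about 0.55 or more. The result should therefore be read from its interval, not from its p-value.

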6.5.2.4 Predictive Biomarker-Analysis Of EoE Transcriptome

In this sub-aim, we aim to identify biomarkers that may predict responsiveness to any or all of the treatment interventions associated with this trial. Determining such a biomarker would have a profound effect on disease management as patients could be quickly triaged into different therapies, e.g. diet versus SGC; thus saving time, reducing the number of endoscopies and potentially improving quality of life issues. As such, in this sub-aim, we will perform the EDP analysis on baseline biopsies, focused on identifying transcript levels that differentiate patients that respond to each of the interventions. In preliminary studies, we have conducted this type of analysis on patients that recently participated in the randomized controlled trial of high dose fluticasone (1760 mcg per day) for the treatment of EoE. Forty-two participants were enrolled in this study (28 FP, 14 placebo). After 3 months, 65% of FP-treated and 0% of placebo-treated participants had complete remission ($P = 0.0001$);

12% of FP-treated and 8% of placebo-treated participants had partial remission. Of the FP-treated participants in complete remission, 73% continued in complete remission, and 20% were in partial remission after halving the daily FP dosage³⁷.

Baseline esophageal gene expression was compared between FP responders and non-responder patients by statistically screening two cohorts of samples before the FP exposure, namely the FP responders and FP-non-responders. A total of 15 genes (Figure 1, $p < 0.05$, fold change > 2.0) on the EDP were identified with a tendency to predict subsequent FP efficacy with CR criteria (≤ 1 eosinophil/HPF in the distal esophagus). It is interesting to note that some of these transcripts include cardinal EoE transcriptome genes such as CCL26 (eotaxin-3) and periostin and CLC (Charcot-Leyden crystals, a marker of eosinophils) suggesting that elevated production was a positive prognostic factor for FP responsiveness; these findings are consistent with a recent report suggesting that more severe tissue inflammation including eosinophil levels was associated with FP responsiveness³⁸. This preliminary result highlights the potential ability of baseline molecular transcripts to differentiate patients but also importance of repeating this analysis with an independent cohort of FP treated patient samples, as preliminarily identified genes have not yet passed the false discovery rate (FDR) correction due to a relatively small n . It is expected that a replication cohort will bring in a higher power to pass the FDR filter. Meanwhile, multiple false-correction methods will be applied to the collective data set, such as the West-Young and Bonferroni methods.

